2.1 Data analysis general information

All analyses will be performed by Novartis or a designated CRO. Any data analysis carried out independently by the investigator should be submitted to Novartis before publication or presentation.

For the Primary CSR at Month 12 analyses, all data until the cut-off date were included. The cut-off day was defined as the Week 53 Day 1 visit date of the last patient (22-Oct-2021).

For the Final CSR at Month 24 analyses, the cut-off date is last patient last visit (LPLV). All data in the clinical database will be used for the analyses.

Data listings will include all data collected up to the cut-off date for the 12-month analysis, or all data recorded in the database for the 24-month analysis.

Continuous variables will be summarized by number of patients, mean, standard deviation, minimum, median, and maximum. For selected parameters, 25th and 75th percentiles will also be presented.

Categorical variables will be summarized by frequencies and percentages.

The 95% confidence interval (CI) using the Clopper-Pearson method will be provided for selected parameters. Kaplan-Meier method will be used for time to event analyses.

2.1.1 General definitions

Investigational drug and study treatment

Investigational drug, study drug and study treatment refer to eltrombopag.

Date of first/last administration of study drug

The date of first administration of study treatment is derived as the first date when a non-zero dose of study treatment was administered as per the Dosage Administration CRF. For the sake of simplicity, the date of first administration of study treatment will also be referred as *start of study treatment*.

The date of last administration of study treatment is defined as the last date when a non-zero dose of study treatment was administered as per Dose Administration (e)CRF. The date of last administration of study treatment is the same as the date of last administration of investigational drug or control drug.

Duration of exposure

The duration of exposure for the **study drug** will be calculated as:

- Duration of study drug exposure (months) = (date of last non-zero dose of study drug) - (first date of study drug) + 1.

For the primary CSR, if the end date was missing for an ongoing patient the cutoff date will be used. The durations will include periods of temporary interruption (planned or actual) for any reason. There will be no ongoing patients for final CSR. Additionally, the duration of exposure for study drug will be computed excluding days of zero dose. The duration of exposure for days without zero dose will be calculated as the sum of all periods with non-zero doses. For each period i without zero dose, exposure will be computed as:

- Duration of exposure for period i (months) = (last date of study drug for period i) - (last date of study drug for period i) + 1.

Dose interruption

An interruption is defined as an actual zero dose on one or more days when the dose is scheduled between two non-zero dosing records.

Note: The last zero dose of a study drug (followed by permanent discontinuation) is not considered as a dose interruption. For the purpose of summarizing interruptions and reasons, in case multiple entries for interruption are entered on consecutive days with different reasons these will be counted as separate interruptions. However, if the reason is the same in these multiple entries on consecutive days, then it will be counted as one interruption.

Dose reduction

A dose reduction is where the prescribed dose is lower than the previous prescribed dose or where the actual dose administered/total daily dose is lower than the prescribed dose. Any dose change to correct a dosing error will not be considered a dose reduction, e.g. if due to a dosing error, a patient receives higher than protocol planned starting dose and moves down to the planned starting dose then this is not counted as a reduction, however if they move directly from a higher than planned starting dose down to a lower than protocol planned starting dose, then this is counted as a reduction.

Note: It is assumed that if there is a dose reduction, then the 'Dose changed' box was ticked on the dose administration eCRF page.

Cumulative dose

Cumulative dose of a study treatment is defined as the total dose given during the study treatment exposure and will be summarized.

The **planned cumulative dose** for a study treatment refers to the total planned dose as per the protocol up to the last date of study drug administration. The planned cumulative dose is not summarized/listed. It is used for relative dose intensity calculations. The **actual cumulative dose** refers to the total actual dose administered, over the duration for which the patient is on the study treatment as documented in the dose administration eCRF. For the patients with sustained response off treatment, the duration will be the time from the start of the treatment to the date of last non-zero dose.

For continuous dosing, the actual cumulative dose is the sum of the non-zero doses recorded over the dosing period and the planned cumulative dose is the planned starting dose summed over the same dosing period.

For patients who did not take any drug, the actual cumulative dose is by definition equal to zero.

Dose intensity and relative dose intensity

Dose intensity (DI) for patients with non-zero duration of exposure is defined as follows:

$DI \text{ (dosing unit / unit of time)} = \text{Actual cumulative dose (dosing unit)} / \text{Duration of exposure (unit of time)}$.

e.g. $DI \text{ (mg/day)} = (50 \text{ mg/day} * 219 \text{ days}) / 365 \text{ days} = 30 \text{ mg/day}$

For patients who did not take any drug the DI is by definition equal to zero.

Planned dose intensity (PDI) is the assigned dose by unit of time planned to be given to patients as per protocol in the same dose unit and unit of time as that of the DI, i.e.

$PDI \text{ (dosing unit / unit of time)} = \text{Planned cumulative dose (dosing unit)} / \text{Duration of exposure (unit of time)}$.

Note that eltrombopag is administered with a tapering regime. Therefore, for some patients, the duration of exposure will not include the time after tapering when they are not getting any dose. The **planned dose** is the starting dose of treatment which was defined for the patient by protocol.

Relative dose intensity (RDI) is defined as follows:

RDI = DI (*dosing unit / unit of time*) / PDI (*dosing unit / unit of time*).

e.g. RDI = DI (92.7 mg/day) / PDI (100 mg/day) = 0.927

Study day

The study day for efficacy (platelet counts) and safety assessments (e.g. adverse event onset, laboratory abnormality occurrence, vital sign measurement, dose interruption etc.) will be calculated as the difference between the date of the event (onset date of an event, assessment date etc.) and the start of study treatment plus 1. The first day of study treatment is therefore study day 1. Example: if start of study treatment is on 05-Jan-2014 and start date of an adverse event is on 09-Jan-2014 then the study day of the adverse event onset is 5. For safety assessments before start of study treatment, the study day is negative and derived by (date of event – start date of study treatment). For example: if start of study treatment is on 05-Jan-2014 and date of lab measurement is on 02-Jan-2014 then the study day of the laboratory abnormality is -3. Note, the day of start of study treatment is day 1, and the day before the date of first study treatment is day – 1, not day 0.

Baseline

The **baseline** is the result of an investigation describing the “true” state of the patient before start of eltrombopag.

The last available assessment on or before the date of start of eltrombopag is taken as “baseline” assessment. In case, assessment is captured pre-dose on first day of eltrombopag (e.g. PROs), this assessment is used for baseline.

On-treatment assessments and observation periods

The overall observation period will be divided into three mutually exclusive segments:

1. **pre-treatment period:** from day of patient’s informed consent to the day before first dose of eltrombopag
2. **on-treatment period:** from date of first dose of eltrombopag to 30 days after the date of the last non-zero dose of eltrombopag (including start and stop date) for patients who completed or discontinued the study early. For ongoing patients, the on-treatment period will be until the cut-off date, as a patient can restart treatment at any time during study.
3. **post-treatment period:** starting at day 30+1 after last non-zero dose of eltrombopag for patients who completed or discontinued the study early. For ongoing patients, there is no post-treatment period.

Safety summaries (tables, figures) include all data considering the on-treatment period definition with the exception of baseline data which will also be summarized where appropriate (e.g. change from baseline summaries). In addition, a separate summary for death including on treatment and post treatment deaths will be provided. In particular, summary tables for adverse events (AEs) will summarize only on-treatment events, with a start date during the on-treatment period (**treatment-emergent** AEs).

However, all safety data (including those from the pre and post-treatment period) will be listed and those collected during the post-treatment period will be flagged.

Additionally, a subgroup analyses on key safety outputs will be provided considering the first 12 months on study. Hence the 12 month on-treatment period is defined as the last non-zero dose + 30 days within the first 12 months on study.

End of Treatment and End of Study

For End of treatment (EOT) derivation, see [Section 2.7.3](#).

Definition of Months and Years

A month will be calculated as $(365.25 / 12) = 30.4375$ days. If duration is to be reported in months, duration in days will be divided by 30.4375. If duration is to be reported in years, duration in days will be divided by 365.25.

For reporting purposes, Month 3 is corresponding to scheduled visit at Week 13 Day1, Month 6 to Week 27 Day 1 visit, Month 9 to Week 39 Day 1, Month 12 to Week 53 Day 1 visit.

Time windows

Time windows for assessments are based on protocol specified windows.

There is a ± 1 day visit window permitted on assessments to take into account scheduling over public holidays, from Week 1 Day 1 to Week 9 Day 1. Also a visit window of ± 3 days is allowed from Week 11 Day 1 to end of treatment.

A visit window of ± 7 days is allowed during the follow-up period for patients with sustained response off treatment.

Time windows for multiple assessments

In order to summarize data of assessments collected over time (including any unscheduled visits), the assessments will be time slotted. If more than one assessment is done within the same time window, the assessment performed closest to the target date will be used. If 2 assessments within a time window are equidistant from the target date, then the earlier of the 2 assessments will be used. If multiple assessments on the same date then the worst case will be used. The end of treatment assessment will be included if collected within 30 days of the last treatment date. Data from all assessments (scheduled and unscheduled), including multiple assessments, will be listed.

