2.4 Treatments (study treatment, rescue medication, concomitant therapies, compliance)

2.4.1 Study treatment / compliance

The number of patients with dose adjustments (reductions, interruption, or permanent discontinuation) and the reasons will be summarized and all dosing data will be listed.

The duration of exposure in months to eltrombopag will be summarized descriptively and will also be categorized in the following intervals: <3 months, 3-<6 months, 6-<9 months, 9-<12 and >=12 months, and less than 1 Month, at least 1 month, at least 2 months, and so on. The duration of exposure excluding days of zero dose will be summarized with the same categorization. The dose intensity and the relative dose intensity will be summarized by means of descriptive statistics. Mean, SD, median, maximum, minimum, 25th percentile and 75th percentile will be provided. Relative dose intensity will also be categorized in the following intervals: <75%, 75-<=90%, 90-<=110%, >110%.

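### SAP 2.1.1 subtracts each dosing period's last date from itself, so exposure excluding zero-dose days would count periods instead of days

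*SAP*

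**What the plan says.** SAP 2.1.1 defines two exposure durations. The overall one is "Duration of study drug exposure (months) = (date of last non-zero dose of study drug) - (first date of study drug) + 1", and it includes interruptions. The second leaves out zero-dose days: "The duration of exposure for days without zero dose will be calculated as the sum of all periods with non-zero doses". For each such period the SAP prints "last date of study drug for period i) - (last date of study drug for period i) + 1". Both formulas are labelled months. Later in 2.1.1, under the definition of months and years, the SAP adds: "If duration is to be reported in months, duration in days will be divided by 30.4375".

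The second duration is reported. SAP 2.4.1 states: "The duration of exposure excluding days of zero dose will be summarized with the same categorization". The bands are under 3, 3 to under 6, 6 to under 9, 9 to under 12, and 12 months or more, plus cumulative one-month steps.

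On dose, SAP 2.1.1 first says that planned cumulative dose "refers to the total planned dose as per the protocol up to the last date of study drug administration". For continuous dosing it then makes planned cumulative dose the starting dose added up over the dosing period. After noting the tapering regimen, it says that the planned dose "is the starting dose of treatment which was defined for the patient by protocol". RDI is banded under 75%, 75–90%, 90–110% and over 110% in 2.4.1, whose heading covers study treatment and compliance.

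**The concern.** The per-period line is an operative analysis formula in the current SAP text, and it feeds a named summary. A programmer or validator who follows it literally would produce a wrong table. Time actually on drug matters in a trial designed to stop drug and, on relapse, restart it. For patients with a treatment-free gap, overall duration includes the gap, and this second summary is meant to remove it.

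A smaller matter of reading goes with it. RDI is measured against the starting dose, while the protocol directs escalation, reduction for high counts, taper and re-treatment. Because RDI appears under a heading that includes compliance, a reader could take a value outside 90–110% as a sign of poor adherence.

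**Working it through.** **The SAP's own examples.** Dose intensity: 50 × 219 / 365 = 30 mg/day, as stated. RDI: 92.7 / 100 = 0.927, as stated. In the first example 219 dosed days are divided by 365 days, so the denominator includes off-drug days. The per-period line plays no part in it.

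**The per-period formula.** As printed: last − last + 1 = 1. As evidently intended: last − first + 1. Months = days / 30.4375 (SAP 2.1.1).

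| Dosing periods | Printed result | Intended days | Intended months | Correct band |
|---|---|---|---|---|
| One, 364 days | 1 | 364 | 11.96 | 9 to under 12 |
| Two, 100 days each | 1 + 1 = 2 | 200 | 200 / 30.4375 = 6.57 | 6 to under 9 |
| Two, 100 and 119 days (7-day gap) | 2 | 219 | 219 / 30.4375 = 7.20 | 6 to under 9 |

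A printed result of 2 falls in the under-3-months band whether it is read as 2 months or as 2 days (2 / 30.4375 = 0.07 months).

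**The overall formula.** It has the correct last-minus-first form and yields days. For 365 days the conversion rule gives 365 / 30.4375 = 11.99 months. Only the unit label is loose.

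**RDI against starting dose, no missed doses.** RDI = cumulative dose / (days from first to last non-zero dose × starting dose). The courses are illustrative and use the protocol's dosing rules (section 6.1, Tables 6-1 and 6-3). Assumptions: two months = 61 days, month 12 = 364 days, and the alternate-day step = 7 doses over 13 days to the last dose.

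- 50 mg for 14 days, then 75 mg to month 12: (700 + 26,250) / (364 × 50) = 1.48.
- 25 mg start, 50 mg after 14 days, 75 mg after a further 14 days, to month 12: (350 + 700 + 25,200) / (364 × 25) = 2.88.
- 50 mg for 14 days, 75 mg for 75 days, then full taper: (700 + 5,625 + 700 + 350 + 175) / (130 × 50) = 1.16.
- 50 mg for 75 days, then full taper: (3,750 + 350 + 175) / (102 × 50) = 0.84.
- 50 mg for 14 days, then 25 mg to month 12: (700 + 8,750) / (364 × 50) = 0.52.
- The 75-day course with taper, 84 days off drug, then 50 mg for 177 days: (4,275 + 8,850) / (364 × 50) = 0.72.
- Constant 50 mg: 1.00.

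For contrast, 50 mg with an unplanned 7-day gap in 226 days gives (50 × 219) / (226 × 50) = 0.97, inside the middle band.

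Not every adherent patient who tapers leaves that band. In the 50 mg taper course the shortfall is 102 × 50 − 4,275 = 825 mg, or 16.5 days at 50 mg. RDI therefore exceeds 0.90 once the course runs longer than 16.5 / 0.10 = 165 days.

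**The case against.** The strongest reply is that this is a typographical slip with an obvious intention. The preceding sentence describes a sum of non-zero-dose periods, and the overall formula just above has the right form. SAP section 1 also places variable derivations in a separate programming specification, which is not among the documents. This stands as far as consequences go: nothing shows that any table was built from the printed line, and a reader should not infer that the primary CSR tables are wrong. The printed formula still needs correcting, because the SAP is the text against which outputs are checked.

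Three stronger readings are tempting, and the documents do not support them.

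- That the months label is a second arithmetic error. SAP 2.1.1 already supplies the division by 30.4375, so what remains is a labelling slip.
- That planned dose is undefined. The opening description is loose, but the operative rule is given twice in 2.1.1, both times as the starting dose, so the calculation is determinate.
- That RDI misclassifies compliant patients. No band is labelled compliant or non-compliant, Protocol 6.6.1 assesses compliance by pill counts and patient information, and Protocol 12.3 lists RDI as a descriptive treatment summary. RDI against starting dose is a legitimate measure of how far titration moved the dose. Using the prescribed dose as denominator is a debatable preference: it would give 100% even where the prescription departed from the protocol.

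**Conclusion.** The per-period exposure formula is wrong as written. It returns 1 for every period, so exposure excluding zero-dose days would equal the number of dosing periods. That conclusion needs no assumption beyond reading the line literally. The size depends on the course: 2 in place of 200 days for two 100-day periods, and 1 in place of 364 days for continuous treatment to month 12.

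The point is minor. It touches one additional descriptive summary on the Safety Set. Overall exposure, dose intensity, RDI, the on-treatment period, the primary endpoint and its test, and the sample size are unaffected.

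The RDI remark is about labelling only. Fully adherent courses run from about 0.5 to 2.9 under the assumptions shown, and the values move with the assumed course.

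**What to change.** In SAP 2.1.1:

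1. Replace the second date in the per-period formula, so that it reads last date minus first date of study drug for period i, plus 1.
2. Write the division by 30.4375 into both formulas labelled months.
3. Reword the opening description of planned cumulative dose to match the starting-dose definition that follows it.

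In SAP 2.4.1, add one sentence saying that RDI is relative to the starting dose, reflects protocol-directed dose changes, and is not a measure of adherence.

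Before the final CSR, confirm that the exposure programs used for the primary CSR did not implement the printed line. If they did, re-run the summary of exposure excluding zero-dose days.

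The cost is a few lines of SAP text and one program check. Protocol 6.7 already requires doses and dose changes to be recorded on the eCRF, so no new data are needed.

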4.6 Risks and benefits

The risks to patients in this study may come from adverse events, adverse events of special interest and lack of efficacy. The risk to patients in this study may be minimized by compliance with the eligibility criteria and study procedures, close clinical monitoring, safety and efficacy assessments as described in [Sections 8.3](#) and [Section 8.4](#); and dose modifications as described in [Section 6.5](#).

There may be unforeseen risks with the study treatment which could be serious. These include but may not be limited to drug to drug interactions and long term safety. Close adherence to eligibility criteria, study procedures safety monitoring, and dose adjustment as described above will help to minimize unforeseen risks. Potential for drug to drug interaction and measures to minimize undesired drug to drug interactions are described in [Sections 6.2.1](#) and [Section 6.2.2](#).

Women of child bearing potential and sexually active males must be informed that taking the study treatment may involve unknown risks to the fetus if pregnancy were to occur during the study, and agree that in order to participate in the study they must adhere to the highly effective contraception requirements outlined in the exclusion criteria. If there is any question that the patient will not reliably comply, they should not be entered or continue in the study.

Risks Associated with Eltrombopag Use

Identified risks as defined by the Risk Management Plan (RMP) for eltrombopag for the ITP indication include hepatotoxicity, thromboembolic events, and post-therapy reoccurrence of thrombocytopenia.

Potential risks as defined by the RMP for eltrombopag for the ITP indication include thrombotic microangiopathy with acute renal failure, increased bone marrow reticulin formation, hematological malignancies, renal tubular toxicity, phototoxicity, and endosteal hyperostosis.

Appropriate eligibility criteria, as well as specific dose modification and stopping rules are included in this protocol. Recommended guidelines for prophylactic or supportive treatment for expected toxicities, including management of study-drug induced adverse events, i.e., hepatotoxicity, thrombotic complications, and ocular changes are provided below.

Hepatotoxicity

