12.5.2 Safety endpoint(s)

Safety summary tables include only data from the on-treatment period with the exception of baseline data which will also be summarized where appropriate.

The on-treatment period lasts from the date of first dose of eltrombopag to 30 days after the date of the last dose of eltrombopag.

Adverse events

All information obtained on adverse events will be displayed by patient. Summary tables for adverse events (AEs) will include only AEs that started or worsened during the on-treatment period, the **treatment-emergent** AEs (TEAEs).

The incidence of TEAEs will be summarized by system organ class (SOC) and or preferred term, severity based on the CTCAE grades, type of adverse event and relation to eltrombopag.

Serious adverse events, AEs leading to discontinuation, AEs leading to dose adjustment and adverse events of special interest (AESI) which includes bleeding events during the on-treatment period will be tabulated.

Specific groupings of AESI will be considered and the number of patients with at least one event in each grouping will be reported. Such groups consists of AEs for which there is a specific clinical interest in connection with eltrombopag treatment or AEs which are similar in nature (although not identical). Note that certain AEs may be reported within multiple groupings/AESIs.

AESIs are defined by MedDRA terms. Definition for retrieval and maintenance is done in the electronic case retrieval sheet (eCRS).

The incidence of AESIs will be summarized by SOC and Preferred Term (PT).

The AESIs as specified in the latest version of the case retrieval sheet (CRS) at the time of analysis will be used.

All deaths (on-treatment and post-treatment [starting at day 30+1 after last dose of eltrombopag]) will be summarized.

All AEs, deaths and SAEs will be listed and those collected during the pre-treatment (from day of patient's informed consent to the day before first dose of eltrombopag) and post-treatment period will be flagged.

A patient with multiple AEs within a primary SOC is only counted once towards the total of the primary SOC.

Clinical laboratory evaluations

Grading of laboratory values will be assigned programmatically as per the CTCAE version 4.03. The calculation of CTCAE grades will be based on the observed laboratory values only, clinical assessments will not be taken into account.

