2.8 Safety analyses

Safety summary tables include all data (from the on-treatment period) with the exception of baseline data which will also be summarized where appropriate.

The on-treatment period lasts from the date of first dose of eltrombopag to 30 days after the date of the last dose of eltrombopag for patients who discontinued the study. For ongoing patients (not applicable for final CSR analysis), the on-treatment period lasts from first dose of eltrombopag to 30 days after the cut-off date. For all safety analyses the safety set will be used.

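### With one on-treatment window per patient in a trial that stops and may restart drug, whether an off-drug adverse event is tabulated depends on later re-treatment

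*SAP*

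**What the plan says.** SAP 2.1.1 sets the on-treatment period, for patients who completed or left the study early, as one block that runs from the first dose "to 30 days after the date of the last non-zero dose of eltrombopag". Nothing restarts it for a second course. For the remaining patients it says: "For ongoing patients, the on-treatment period will be until the cut-off date, as a patient can restart treatment at any time during study", and "For ongoing patients, there is no post-treatment period". SAP 2.8 gives those same patients a different end: "the on-treatment period lasts from first dose of eltrombopag to 30 days after the cut-off date". For the final report, SAP 2.1.1 states: "There will be no ongoing patients for final CSR".

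Protocol 12.5.2 uses the same single block, has no rule for ongoing patients, and says: "Safety summary tables include only data from the on-treatment period". Post-treatment events go to flagged listings; only deaths have a summary covering both periods (SAP 2.1.1 and 2.8.2). The 12-month safety window in SAP 2.1.1 also ends 30 days after the last non-zero dose.

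SAP 2.8.1 reports treatment-emergent events as numbers and percentages of patients and splits the adverse-event overview by SRoT_M12 status. Protocol 6.1.3 and 9.3 offer re-treatment up to month 24 and follow month-12 responders quarterly, including for adverse events.

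**The concern.** A window ending 30 days after the last dose suits one continuous course. Here stopping is the aim and restarting is allowed, so the last dose may come long after an event that occurred off drug. Classification then depends on what happens later.

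Take two month-12 responders with the same bleeding event in follow-up, both long off drug. One restarts eltrombopag, the window stretches back over the bleed, and it enters the bleeding AESI table. The other receives a different therapy and leaves the study (Protocol 9.3), so the bleed is post-treatment and is only listed as an adverse event.

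At stake are the AE, SAE and AESI tables and the overview by SRoT_M12 status. These give crude percentages over windows whose length depends on outcome, with no person-time. The off-drug period also matters for safety in itself: Protocol 4.6 names as identified risks "hepatotoxicity, thromboembolic events, and post-therapy reoccurrence of thrombocytopenia", and the last of these arises only after stopping.

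**Working it through.** **Plan's own figure.** The dose-intensity example in SAP 2.1.1 is 50 mg/day × 219 days / 365 days = 30 mg/day. It reproduces exactly, and only if the 365 − 219 = 146 zero-dose days stay in the denominator; without them the result is 50. The main exposure measure therefore includes drug-free days, as the on-treatment window does.

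**Windows.** All patient dates below are assumptions. A month is 30.4375 days (SAP 2.1.1), so month 24 is about day 730. The window end is the last dose day + 30.

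| Assumed patient | Last dose (day) | Window ends (day) | Off-drug days inside, beyond 30-day margin | Days to 730 outside |
|---|---|---|---|---|
| SRoT_M12, stops day 97, never restarts | 97 | 127 | 0 | 603 (83%) |
| SRoT_M12, stops day 183, never restarts | 183 | 213 | 0 | 517 (71%) |
| SRoT_M12, stops day 335, never restarts | 335 | 365 | 0 | 365 (50%) |
| SRoT_M12, stops day 183, restarts day 548 | 730 | 760 | 334 | 0 |
| Not SRoT_M12, on drug to month 12 | 365 | 395 | 0 | not followed further |

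Day 97 is about the earliest stop: complete response on day 8, plus 61 days of maintenance, plus a 28-day taper from 50 mg.

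For the re-treated patient, the gap is 548 − 183 − 1 = 364 days, and 364 − 30 = 334. Dosing days are 183 + 183 = 366 of 730, so half of main exposure is drug-free. With a window per course, on-treatment time is (183 + 30) + (183 + 30) = 426 days, and 760 − 426 = 334 days move to off-drug time.

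**One event across the outputs.** Stop on day 183; non-fatal event on day 300.
- Primary CSR, patient ongoing at cut-off: treatment-emergent.
- Final CSR, never re-treated: post-treatment, because the window closed on day 213.
- Final CSR, re-treated from day 548: treatment-emergent in the main tables. It is outside the 12-month tables, where the last dose within 12 months is still day 183 (natural reading of SAP 2.1.1).

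**The 12-month window.** Stop day 183, restart day 300, last dose day 365. The gap is 300 − 183 − 1 = 116 days, and 116 − 30 = 86 off-drug days still count as on-treatment. Gaps closed within 12 months are not removed.

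**Ongoing patients.** SAP 2.1.1 ends their window at the cut-off and SAP 2.8 at the cut-off + 30 days. SAP 2.1 includes data only to the cut-off in the primary analysis, so the difference should matter little for counts, but the two sections cannot both be right.

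**The case against.** Much of the off-drug safety picture is tabulated elsewhere. A reader might infer that bleeding and recurrence more than 30 days after stopping appear only in listings. The documents do not support that:
- The primary endpoint fails on a count below 30 × 10⁹/L or a bleeding AE up to month 12 (SAP 2.5.1 and 2.5.2).
- Kaplan-Meier analyses 1b and 1c count these events to month 24, and items 2 and 6 tabulate response and maintained counts to month 24 (SAP 2.7.2).
- Bleeding AEs for efficacy are drawn from all AEs, excluding only those on or before day 7 (SAP 2.8.4.4).

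Deaths are summarised in both periods. Exposure without zero-dose days is planned with the same categories (SAP 2.1.1 and 2.4.1), although its per-period formula, as printed, subtracts a date from itself and needs correcting. The 30-day rule is pre-specified, and no safety test depends on it.

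Two further inferences also fail. Multiplying 25% by 105 gives about 26 patients, but that is the responder count under the design alternative, not a count of anyone affected. And the contrast between the re-treated patient and the lasting responder, both stopping on day 183, lies within the SRoT_M12 column, not between columns.

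All of that stands. It leaves three things unanswered. The efficacy analyses count bleeding within composite failure events, without term, grade or seriousness, and do not cover other non-fatal AEs. The exposure measure without zero-dose days has no counterpart for AEs. And the overview columns still differ in window: in the working, 395 days outside SRoT_M12 against 213 or 760 within it.

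**Conclusion.** The concern holds for AE, SAE and AESI tabulation, not for the efficacy evidence on bleeding and relapse or for the primary result. One block per patient makes drug-free gaps treatment-emergent time in re-treated patients, and leaves non-fatal off-drug AEs beyond 30 days only listed in patients not re-treated.

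Under the assumed stop dates, 50% to 83% of 24 months falls outside the AE tables for a lasting responder. For a patient re-treated from day 548, 334 of 760 window days are off drug beyond the margin. These are illustrations per patient. The documents do not give the numbers re-treated after a gap, or off drug and ongoing on 22-Oct-2021, so the total effect cannot be sized.

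The change of status between reports rests on the current SAP's account of the primary analysis; the SAP version in force then is not among the documents. The change is worth making in the final CSR.

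**What to change.** Keep the standard on-treatment table. For the final CSR:
- Derive a per-course flag: each course's first dose to its last dose + 30 days is on-drug, and all other time after first dose is off-drug.
- Add AE, SAE and bleeding-AESI tables for on-drug and off-drug time, with patient-years, overall and by SRoT_M12 status.
- Apply the same flag to the first-12-month outputs in that report.
- Footnote events whose status differs from the primary CSR. That report was already final (SAP 1), so one rule cannot now be imposed on both.
- Reconcile SAP 2.1.1 with SAP 2.8 on where the window ends for ongoing patients.

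The cost is one derived variable and two or three extra tables, with no new data, since dose changes are already recorded. The tables need a caveat: visits are biweekly to month 12 but quarterly afterwards, so on-drug and off-drug rates are not fully like-for-like.
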